8.3 FUTILITY ANALYSIS

A futility analysis will be performed when 210 patients are recruited (i.e., ~105 patients enrolled in each arm). The recruitment will not be put on hold. The IDMC will review efficacy and safety data available at that time and, based on the observed results, might recommend stopping the trial.

Following the prospective assumptions, this futility analysis will occur before one year after start of recruitment. The significance level will be determined by the actual observed number of events, and type II error will be controlled by O'Brien-Fleming boundaries.

8.4 INTERIM SAFETY ANALYSIS

An interim safety analysis, performed when 40 patients are enrolled in the PM01183 arm (Arm A), will test if the addition of primary CSF prophylaxis might be necessary. With the information available at that time, a Bayesian test assuming non-informative prior distribution will be done to assess the null hypothesis of febrile neutropenia $\leq 20\%$ versus the alternative hypothesis of febrile neutropenia $>20\%$. If the probability associated with the alternative hypothesis is higher than 50% (e.g., 8 cases out of 40 patients), the addition of primary CSF prophylaxis would be considered necessary.

At the time of the interim safety analysis, recruitment in the control arm (Arm B, PLD and topotecan) is also expected to be 40 patients.

The IDMC may request to review other preliminary safety/efficacy parameters, but no claim of superiority will be done; therefore, no type I/II error corrections will be applied.

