7.2 SAFETY

Patients will be evaluable for safety if they have received any partial or complete treatment infusion. All AEs will be graded according to the NCI-CTCAE v.4. Treatment delays, dose reduction requirements and reason for treatment discontinuation will be monitored throughout the study.

The safety profile of patients will be monitored throughout the treatment and up to 30 days after the last treatment infusion (end of treatment, EOT), or until the patient starts a new antitumor therapy or until the date of death, whichever occurs first.

Any treatment-related AEs will be followed until recovery to at least grade 1 or stabilization of symptoms, whichever occurs first.

An interim safety analysis will be performed by the IDMC after the recruitment of the first 40 patients in the PM01183 arm (Arm A) to assess if the addition of primary CSF prophylaxis might be necessary. Although febrile neutropenia did not occur in the first-in-human PM01183 single-agent study, based on pooled data available from all ongoing phase II studies at 7.0 mg FD, it occurred in about 16% of patients. In this clinical trial, the expected percentage of febrile neutropenia is lower, as the PM01183 dose will be administered based on BSA and at a dose (3.2 mg/m²) below the RD found in the first-in-human PM01183 trial (4.0 mg/m² = 7.0 mg FD).

Furthermore, PM01183, PLD and topotecan dose will be capped at a BSA of 2.0 m² in those patients who have a greater BSA.

At the time of the interim safety analysis, recruitment in the control arm (Arm B, PLD and topotecan) is also expected to be 40 patients.

Safety evaluations will be also performed by the IDMC during the futility analysis to be conducted in all treatment arms once 210 patients are recruited.

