3.2 Safety Population

Safety population or “all treated patients” population will be defined as patients who have received at least part of one infusion of the investigational agents, and analyzed in the group where they were treated.

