The IDMC may request to review other preliminary safety/efficacy parameters, but no claim of superiority will be done; therefore, no type I/II error corrections will be applied.

5.2.2 *Interim Safety Analysis*

An interim safety analysis, performed when 40 patients are enrolled in Arm A, will test if the addition of primary CSF prophylaxis might be necessary in this arm. With the information available at that time, a Bayesian test assuming non-informative prior distribution will be done to assess the null hypothesis of febrile neutropenia $\leq 20\%$ vs. the alternative hypothesis of febrile neutropenia $>20\%$. If the probability associated with the alternative hypothesis is higher than 50% (e.g., 8 cases out of 40 patients), the addition of primary CSF prophylaxis will be considered necessary.

At the time of the interim safety analysis, recruitment in Arm B (PLD or topotecan) is also expected to be approximately 40 patients.

The IDMC may request to review other preliminary safety/efficacy parameters, but no claim of superiority will be done; therefore, no type I/II error corrections will be applied.

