12.3.2 Interim Bayesian Safety Analysis

For PM01183 a bayesian test assuming non-informative prior distribution will be done to assess the null hypothesis of febrile neutropenia < 20% *versus* the alternative hypothesis of febrile neutropenia \geq 20%. If the probability associated with the alternative hypothesis is higher than 50%, at the interim analysis with the first 40 patients treated in arm A, the addition of primary CSF prophylaxis will be considered necessary.

Table 12.3.2.1 Bayesian test

	Probability of being under null hypothesis	Probability of being under alternative hypothesis
Observed Proportion		

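### The febrile-neutropenia interim sets no minimum follow-up, so read literally it counts patients not yet past the second-week nadir as event-free and leans towards not triggering

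*Protocol*

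**What the plan says.** Protocol 8.2.2 and 8.4 tie the look to a head count: "An interim safety analysis, performed when 40 patients are enrolled in the PM01183 arm (Arm A"). They add that "With the information available at that time, a Bayesian test assuming non-informative prior distribution will be done". The rule is met when the posterior probability of a rate above 20% exceeds 50%, and the worked example is 8 cases in 40.

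Other places word the trigger differently:

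- SAP 5.2.2: "An interim safety analysis, performed when 40 patients are enrolled in Arm A".
- Protocol 7.2: "after the recruitment of the first 40 patients in the PM01183 arm (Arm A").
- SAP 12.3.2: "at the interim analysis with the first 40 patients treated in arm A".

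Patients who were never dosed are excluded elsewhere. Protocol 7.2 says: "Patients will be evaluable for safety if they have received any partial or complete treatment infusion". SAP 3.2 defines the safety population as "patients who have received at least part of one infusion of the investigational agents". Evaluability therefore needs part of one infusion and nothing more. No section requires a completed Cycle 1, a number of days on study or a stated data cutoff. Recruitment stays open during the look (protocol 3), and operational details are left to the IDMC charter (protocol 3; SAP Appendix I).

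The hypotheses also differ slightly. Protocol 8.4 and SAP 5.2.2 put exactly 20% in the null, whereas SAP 12.3.2 has "the null hypothesis of febrile neutropenia < 20" per cent. The non-informative prior is not named.

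**The concern.** Protocol 1.2.1.3 places the nadir in the second week after dosing. A patient dosed a few days before the cut adds one to the denominator and almost nothing to the numerator, so the bias has one direction.

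The rule has little slack: at 40 patients, one missed event turns a trigger into a non-trigger. The look exists because the phase II ovarian study saw a rate slightly over 20% (protocol 1.5; 21.2% in 1.3.1), so the rule has to work near 20%, where missing follow-up does most damage. A missed trigger has a consequence: protocol 6.7.2 prohibits primary CSF prophylaxis in Arm A unless the IDMC recommends it after this analysis.

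**Working it through.** **1. The plan's own figure.** With x cases in n patients and a Beta(a, a) prior, the posterior is Beta(a + x, a + n - x).

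| Cases | P(rate > 20%), uniform (a = 1) | Jeffreys (a = 0.5) |
|---|---|---|
| 8/40 | 0.562 | 0.516 |
| 7/40 | 0.407 | 0.359 |

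The 8/40 example is reproduced, and 8 is the minimum under both priors. Moving exactly 20% from one hypothesis to the other changes nothing under a continuous posterior.

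**2. Fully followed behaviour.** P(X >= 8 | n = 40) is 0.304 at a true 16%, 0.635 at 21.2% and 0.818 at 25%.

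**3. How many patients are immature.** Planned Arm A accrual is 420 / 18 / 2 = 11.67 per month. On the day of the 40th enrolment, if dosing is immediate, that patient has no follow-up. About 11.67 x 7/30.4 = 2.7 others are in their first week and 2.7 in their second. If events fall evenly over days 7-14, second-week patients have on average shown half their events. The loss is equivalent to 1 + 2.7 + 1.35 = about 5 patients with no follow-up. With 35 effectively followed, P(X >= 8 | n = 35, 21.2%) = 0.471. To reach 8 cases the observed rate among those 35 must be 8/35 = 22.9%.

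**4. Simulation.** Staggered Poisson entry, 100,000 runs, 0 or 3 days from enrolment to first dose, undosed patients excluded, uniform prior applied to the realised denominator, all events on days 7-14 of Cycle 1. Ranges span the two dosing lags.

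| Cut after 40th enrolment | Chance of triggering at a true 21.2% |
|---|---|
| same day | 47-48% |
| +7 days | 52-56% |
| +14 days | 62-63% |
| +21 days | 64% |
| fully followed | 64% |

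- Same-day cut at a true 25%: 67-68%, against 82% fully followed.
- Same-day cut at a true 16%: 19-20%, against 30%.
- Half the accrual, same-day, 21.2%: about 53-54%.
- Only 70% of events in Cycle 1 and the rest in Cycles 2-3, 21.2%: about 34-36% same-day and 54-55% at +21 days.

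**5. Same-day look, counting only matured patients.** Requiring at least 14 days from first infusion leaves a mean of 32.5-33.6 patients; requiring 21 days leaves 29.8-30.9. With all events in Cycle 1, the chance of triggering is about 63% at 21.2%, 79-80% at 25% and 33-35% at 16%. At these denominators the prior can decide the result: 7/36 gives 0.533 (uniform) but 0.484 (Jeffreys).

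**The case against.** The case against is mainly about stakes, and much of it stands.

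- **The text does not require a same-day freeze.** Protocol 7.2 places the look after recruitment, SAP 12.3.2 says treated, and an IDMC needs time to be supplied with data. If the cut falls two weeks or more after the 40th enrolment, almost nothing is lost to Cycle 1 events.
- **The charter may already set a cutoff.** It was not available here.
- **The expected rate is lower.** Protocol 1.5 expects a rate below the pooled 16%, and section 1.4 reports 4% at or below 3.2 mg/m2 (23 patients). At such rates the bias rarely changes the outcome.
- **Accrual is an 18-month mean.** A slow start-up means fewer immature patients.
- **Other safeguards exist.** Each episode is reported within 24 hours (7.4.1). Secondary CSF prophylaxis is required after febrile neutropenia if treatment continues without dose reduction (6.6). Safety is reviewed periodically (7.5) and again at 210 patients, and the IDMC may ask for other data.

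None of these supplies a follow-up requirement. Rapid reporting removes reporting lag, not missing observation time.

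Two stronger readings are tempting. From the word enrolled, a reader might infer that undosed patients also dilute the denominator; with a 3-day dosing lag that would put the same-day figure at 21.2% at 43%. Protocol 7.2 and SAP 3.2 exclude those patients, so that figure does not apply. A reader might also infer that the differing hypotheses change the decision; step 1 shows that they do not.

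**Conclusion.** The point holds as a gap in a stated decision rule. Followed literally, the rule counts patients who have not passed the nadir as event-free, and this can only push it towards not triggering. At a true 21.2% the same-day loss is about 16-17 percentage points (64% to 47-48%), and at 25% about 14-15 points (82% to 67-68%). It is material only with a cut within about a week of the 40th enrolment and a true rate near or above 20%.

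The documents do not support saying that the interim will miss a real problem: they fix no cut date, and the charter may. The size rests on planned accrual, a uniform prior and event timing on days 7-14. That timing is an assumption, because the second-week nadir is a neutropenia observation from a first-in-human study that saw no febrile neutropenia. Events in later cycles would be truncated in the same direction. This is worth considering, with medium confidence; it is not a defect that undermines the trial.

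**What to change.** State identically in protocol 8.2.2 and 8.4 and SAP 5.2.2 and 12.3.2, cross-referenced to the IDMC charter, that the test uses the first 40 treated Arm A patients, with data cut once each is at least 21 days from first infusion. This keeps n = 40 and the 8/40 example. Apply the window whether or not treatment has stopped, and say how deaths or new antitumor therapy inside it are counted.

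Cost: wording changes, and a look about 3-4 weeks after the 40th enrolment. By then 11.67 x 21/30.4 = 8.1 to 11.67 x 28/30.4 = 10.7 more Arm A patients will have enrolled. Against a same-day cut, the chance of triggering at a true 16% rises from 19-20% to 30%, which is the rule's own fully followed behaviour.

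Alternatively, keep the timing and count only patients at least 14 or 21 days from first infusion. Select them on time since first infusion alone and report earlier events separately. Adding early events without the event-free patients dosed alongside them would overshoot (at a true 16%, 36-37% with 14 days and 44-45% with 21 days). Name the prior. This avoids delay but tests about 30-34 patients and triggers 33-35% of the time at a true 16%, against 30% fully followed.

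Neither option fully captures later-cycle events. As housekeeping, use one wording of the hypotheses in both documents. Leave the 20% threshold, the 50% criterion and the IDMC's action unchanged.

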9. ADMINISTRATIVE SECTION

9.1 ETHICS

This clinical trial will be conducted in accordance with the ethical principles that have their origin in the World Medical Association (WMA) Declaration of Helsinki (see [APPENDIX 4](#)) and will be consistent with GCP guidelines and pertinent regulatory requirements.

The study personnel involved in conducting this trial will be qualified by education, training and experience to perform their respective task(s).

The study will be conducted in compliance with the protocol. The protocol, any amendments and the patient informed consent will receive IEC/IRB approval/favorable opinion prior to initiation, according to pertinent regulations.

The decision of the IEC/IRB concerning the conduct of the study will be made in writing to the Investigator, and a copy of this decision will be provided to the Sponsor before the beginning of the study.

The Investigator and/or the Sponsor is/are responsible for keeping the IEC/IRB informed of any significant new information about the study drug.

All protocol amendments will be agreed upon by the Sponsor and the Investigator.

Administrative changes of the protocol are minor corrections and/or clarifications that have no impact on the way the study is to be conducted.

9.2 MONITORING, AUDITING AND INSPECTING

The study will be monitored by regular site visits and telephone calls to the Investigator by the clinical trial monitor designated by Pharma Mar S.A.

During site visits, the trial monitor should revise original patient records, drug records and document retention (study file). Additionally, the trial monitor should observe study procedures and will discuss any problems with the Investigator.

Adequate time for these visits should be allocated by the Investigator. The Investigator should also ensure that the monitor is given direct access [as per International Conference on Harmonization (ICH) Topic E6 (R1) Guideline for Good Clinical Practice, Sections 4.9.7 and 6.10] to source documents (i.e., hospital or private charts, original laboratory records, appointment books, etc.) of the patient which support data entered in the case report forms, as defined in the ICH Topic E6 (R1) Guideline for Good Clinical Practice, Sections 1.51 and 1.52.

Systems and procedures will be implemented to ensure the quality of every aspect of the trial.

During the course of the trial, the Clinical Quality Assurance Department of Pharma Mar S.A. or external auditors contracted by the Sponsor may conduct an onsite audit visit (ICH Topic E6 (R1) Guideline for GCP, Section 1.6).

Participation in this trial implies acceptance of potential inspection by national or foreign Competent Authorities.

9.3 PATIENT INFORMED CONSENT

The rights, safety and well-being of the trial patients are the most important considerations and should prevail over interests of science and society.

The ICFs will include all elements required by ICH, GCP and applicable regulatory requirements.

Prior to inclusion into the trial, the Investigator or a person designated by the Investigator, must provide the patient with one copy of the Informed Consent Forms (ICFs). This copy must provide written full information about the clinical trial, in a language that is non-technical and easily understood, as well as on the sub-study (PGx and pharmacogenetic). The Investigator should allow the necessary time for the patient or his/her legally acceptable representative to inquire about the details of the clinical trial; then, the ICFs must be freely signed and personally dated by the patient and by the person who conducted the Informed Consent discussion before the beginning of the study. The patient should receive a copy of the signed ICFs and any other written information provided to study patients prior to participation in the trial.

During a patient's participation in the trial, any updates to the consent forms and any updates to the written information will be provided to him/her.

If there is a need to obtain new consent from the patients, the Investigator or a person designated by the Investigator should inform the patients of any new information relevant to the patients' willingness to continue participation in the study, before obtaining the written consent.

9.4 CONFIDENTIALITY/ PATIENTS IDENTIFICATION

The collection and processing of personal data from the patients enrolled in this clinical trial will be limited to those data that are necessary to investigate the efficacy, safety, quality and usefulness of the study drug used in this trial.

It is the Investigator's responsibility that sufficient information on the identity of the patients will be retained.

The trial monitor, the Sponsor's auditor, the IECs/IRBs and the Competent Authorities should have direct access to all requested trial-related records, and agree to keep the identity of study patients confidential.

The data must be collected and processed with adequate precautions to ensure confidentiality and compliance with applicable data privacy protection laws and regulations.

Explicit consent for the processing of personal data will be obtained from the participating patient before data collection, if applicable, and this consent should also address the transfer of the data to other entities and countries.

Pharma Mar S.A. shall comply with the Directive 95/46/EEC of the European Parliament and of the Council of 24 October 1995 on the protection of individuals with regard to the processing of personal data and on the free movement of such data.

9.5 CASE REPORT FORMS

Electronic CRFs will be used to record all data for each patient. It is the responsibility of the Investigator to ensure that the CRFs are properly and completely filled in, in English. CRFs must be completed for all patients who have given their informed consent.

A patient's source documentation is the patient's records (including but not limited to physician/hospital notes, nurses notes, IMP preparation records including reconstitution and dilution, IMP administration records, patient-reported outcomes, etc.) and any original document, and as such they should be maintained at the study site.

The data collected in the CRF will be entered into databases, which comply with the Spanish Act implementing the Directive 95/46/EC of the European Parliament and of the Council of 24 October 1995 on the protection of individuals with regard to the processing of personal data.

9.6 INSURANCE

The Sponsor will provide insurance or indemnity in accordance with the applicable regulatory requirements.

9.7 RETENTION OF RECORDS

The Investigator/Institution should maintain trial documents according to Section 8 of the ICH Topic E6 (R1) Guideline for Good Clinical Practice and as required by applicable regulatory requirements.

Essential documents should be retained as per the aforementioned ICH guideline or for a longer period of time, if required by the applicable regulations.

9.8 USE OF INFORMATION AND PUBLICATION

Before the investigators of this study submit a paper or abstract for publication or otherwise publicly disclose information concerning the study drug or products, Pharma Mar S.A. must be provided with at least 60 days to revise and approve the proposed publication or disclosure to ensure that confidential and proprietary data are protected.

If Pharma Mar S.A. determines that patentable patient matter is disclosed in the proposed publication or disclosure, the publication or disclosure will be withheld for a period of time considered convenient. If the study is part of a multicenter study, the first publication of the study shall be made in conjunction with the presentation of a joint, multicenter publication of the study results with the investigators and the institutions from all appropriate sites that are contributing data, analysis and comments. However, if such a multicenter publication is not submitted within 12 months after conclusion, abandonment or termination of the study at all sites, the present study may be published individually in accordance with the procedure established above.

The order of the coauthors will reflect the relative contribution of each one to study development and analysis. In general, the first author will be the investigator who recruits the highest number of patients with information finally available for data analysis. Relevant Pharma Mar S.A. personnel who have fully participated in the study must be considered for co-authorship of the publication.

11. APPENDICES

APPENDIX 1: ECOG PERFORMANCE STATUS ASSESSMENT SCALE

Grade	ECOG PS*
0	Fully active, able to carry on all pre-disease performance without restriction
1	Restricted in physically strenuous activity but ambulatory and able to carry out work of a light or sedentary nature, e.g., light house work, office work
2	Ambulatory and capable of all self-care but unable to carry out any work activities. Up and about more than 50% of waking hours
3	Capable of only limited self-care, confined to bed or chair more than 50% of waking hours
4	Completely disabled. Cannot carry on any self-care. Totally confined to bed or chair
5	Dead

*As published in Am. J. Clin. Oncol 5:649-655, 1982: Oken, M.M., Creech, R.H., Tormey, D.C., Horton, J., Davis, T.E., McFadden, E.T., Carbone, P.P.: *Toxicity And Response Criteria Of The Eastern Cooperative Oncology Group*.

APPENDIX 2: EVALUATION OF RESPONSE. THE RECIST.

This document summarizes the main information contained in RECIST version 1.1.

*Further details can be found in the original article: Eisenhauer EA, Therasse P, Bogaerts J, et al.: New response evaluation criteria in solid tumours: revised RECIST guideline (version 1.1). Eur J Cancer 2009; 45(2): 228-247.*²

LIST OF ABBREVIATIONS

CR	Complete Response
CRF	Case Report Form
CT	Computed Tomography
FDG-PET	Fluorodeoxyglucose-Positron Emission Tomography
MRI	Magnetic Resonance Imaging
NE	Not Evaluable
PD	Progressive Disease
PET	Positron Emission Tomography
PFS	Progression-free Survival
PR	Partial Response
PSA	Prostate-specific Antigen
RECIST	Response Evaluation Criteria in Solid Tumors
SD	Stable Disease
TPP	Time to Progression

LIST OF TABLES

Table 1. Summary of major changes from RECIST 1.0 to RECIST 1.1.³

Table 2. Time point response: patients with target (+/-non-target) disease.

Table 3. Time point response: patients with non-target disease only.

Table 4. Best overall response when confirmation of complete response (CR) and partial response (PR) is required.

² A summary of major changes from RECIST 1.0 to RECIST 1.1 can be found at the beginning of this document (**Table 1**).

³ This table is named Appendix I in the original RECIST 1.1 article.

The main changes from RECIST 1.0 to RECIST 1.1 are shown in the following table.

Table 1. Summary of major changes from RECIST 1.0 to RECIST 1.1.

RECIST 1.0	RECIST 1.1	Rationale
Minimum size measurable lesions	CT: 10 mm spiral 20 mm non-spiral	CT 10 mm; delete reference to spiral scan
	Clinical: 20 mm	Clinical: 10 mm (must be measurable with calipers)
	Lymph node: not mentioned	CT: ≥ 15 mm short axis for target ≥ 10–<15 mm for non-target < 10 mm is non-pathological
Special considerations on lesion measurability	–	Notes included on bone lesions, cystic lesions
Overall tumor burden	10 lesions (5 per organ)	5 lesions (2 per organ)
Response criteria target disease	CR lymph node not mentioned	CR lymph nodes must be <10 mm short axis
	PD 20% increase over smallest sum on study or new lesions	PD 20% increase over smallest sum on study (including baseline if that is smallest) and at least 5 mm increase or new lesions
Response criteria non-target disease	‘Unequivocal progression’ considered as PD	More detailed description of ‘unequivocal progression’ to indicate that it should not normally trump target disease status. It must be representative of overall disease status change, not a single lesion increase
New lesions	–	New section on New lesions
		To provide guidance on when a lesion is considered new (and thus PD)

RECIST 1.0	RECIST 1.1	Rationale
Overall response	Table integrated target and non-target lesions Two tables: one integrating target and non-target and the other of non-target only Special notes: How to assess and measure lymph nodes CR in face of residual tissue Discussion of 'equivocal' progression	To account for the fact that RECIST criteria are now being used in trials where PFS is the endpoint and not all patients have measurable (target) disease at baseline Frequently asked questions on these topics
Confirmatory measure	For CR and PR: criteria must be met again 4 weeks after initial documentation Retain this requirement ONLY for non-randomized trials with primary endpoint of response	Data warehouse shows that response rates rise when confirmation is eliminated, but the only circumstance where this is important is in trials where there is no concurrent comparative control and where this measure is the primary endpoint
Progression-free survival	General comments only More specific comments on use of PFS (or proportion progression-free) as phase II endpoint Greater detail on PFS assessment in phase III trials	Increasing use of PFS in phase III trials requires guidance on assessment of PD in patients with non-measurable disease
Reporting of response results	9 categories suggested for reporting phase II results Divided into phase II and phase III 9 categories collapsed into 5 In phase III, guidance given about reporting response	Simplifies reporting and clarifies how to report phase II and III data consistently
Response in phase III trials	More relaxed guidelines possible if protocol specified This section removed and referenced in section above: no need to have different criteria for phase II and III	Simplification of response assessment by reducing number of lesions and eliminating need for confirmation in randomized studies where response is not the primary endpoint makes separate 'rules' unnecessary
Imaging appendix	Appendix I Appendix II: updated with detailed guidance on use of MRI, PET/CT Other practical guidance included	Evolving use of newer modalities addressed. Enhanced guidance in response to frequent questions and from radiology review experience
New appendices		Appendix I: comparison of RECIST 1.0 and 1.1 Appendix III: frequently asked questions

RECIST 1.0	RECIST 1.1	Rationale
------------	------------	-----------

CR, complete response; CT, computed tomography; MRI, magnetic resonance imaging; RECIST, response evaluation criteria in solid tumors; PD, progressive disease; PET, positron emission tomography; PFS, progression-free survival; PR, partial response.

